Obtain informed consent. Screen potential participants by inclusion and exclusion criteria; obtain medical history, document. **Total N = 48**

Visit 1

Time Point

Weekly GSSC data collection

Visit 2
Time Point

4 weeks: collect blood and stool. Administer 38-point Gastrointestinal Symptom and Severity Checklist (GSSC) Questionnaire (FFQ)

Analyses: (a) Evaluation of inflammation and intestinal barrier function in serum; (b)

4.1.Treatment Design

Dose rationale. The intervention will include a dose ranging between 10 to 15 g daily as previously reported¹⁰. Doses were selected based on previous literature reports^{16, 17, 28-30} and the interventions conducted by our group to assess efficacy of GOS in lactose-intolerant individuals^{10, 11, 31, 32}. The hGOS preparation will be composed of GOS enriched with LacNac at a concentration of 6.7-31 μ g/mL (<1% of the formulation), which is in the range found in human breast milk³³ and hence considered safe.

Regimen. The prebiotics dose will be 5 grams twice daily on days 1–10 followed by 7.5 grams twice daily on days 11–28. The placebo (powdered corn syrup comprised of fructose, glucose, and an inert cellulose material that matched the consistency, color, sweetness, and taste of the prebiotics) will be administered in a blinded matching packet at the same doses. If participants miss taking a dose on a given day, they will be directed to put the pouch for that day aside, and on the next day take the next numbered pouch.

4.2.Experimental / Observational Design

Subjects will be assigned randomly to one of 3 groups (n = 16): GOS, hGOS or placebo.

4.3.Measurement Design

Blood and stool samples will be collected at baseline (Day 0) and end of treatment (Day 28). Stool collection kits will be provided to participants in case samples cannot be obtained *during study visits*. Safety and tolerability will be determined based on the severity and/or frequency of side effect using a 38-point Gastrointestinal Symptom and Severity Checklist (GSSC). In addition, tolerability will be evaluated through occurrence of drop-out and adherence.

Measurements on blood (10 mL per visit for a total of 20 mL):

- (1) Fasting venous blood samples will be drawn and serum will be used to quantify zonulin using the Zonulin (IDK® Zonulin) (Serum) ELISA test (Immundiagnostik AG).

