6.6. Compliance Checks

Participant adherence will be monitored weekly via email and/or text messages through self-reporting of number of treatment pouches left.

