6.7. Withdrawal / Discontinuation of Enrolled Participants

At baseline and every week after for the duration of the study, participant will answer a 33 question gastrointestinal symptom assessment with the PROMIS Gastrointestinal Symptom Scale (Spiegel, et al, Am J Gastrol, 2014). If a subject experience and increase in 2 levels over baseline in their response to questions 2 (abdominal pain), 6 (abdominal discomfort), 8 (constipation), 16 (diarrhea), 22 (abdominal distention), 26 (abdominal bloating), 31 (nausea), or 33 (vomiting) on the PROMIS Gastrointestinal Symptom Scale, they will be a) withdrawn from the study if the participant is in the first 10 days of their participation, or b) asked to go back to the lower dose of 5g sachets twice daily and reassessed in 3 days, if the participant has passed day 10 of participation. If participants are able to tolerate the lower dose, they will continue participating in the trial albeit consuming the lower dose of the prebiotic treatment. Likewise, if a participant develops a condition that is an exclusion criterion or participant noncompliance increases risk of decreased study integrity, the participant will be withdrawn from the study.

If 5 of the first 20 subjects enrolled experience a change of 2 levels on questions 2, 6, 8, 16, 22, 26, 31, 33 on the PROMIS Gastrointestinal Symptom Scale (bloating, flatulence, watery stools, abdominal pain) compared to baseline or higher adverse event leading to subject discontinuation, we will stop the study temporarily and request the medical monitor to do an unblinded assessment of the data. The medical monitor (unblinded) will assess subjects who discontinued due to the specified adverse effects to determine if they are all in one arm of the study or range across arms. The medical monitor will assess if there is a safety signal in a specific arm or treatment dose over the other that warrants the closure of the study. Since the medical monitor will be the person determining continuation or discontinuation of the study, the study team will remain blinded and unbiased.

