7.8. Premature Discontinuation

If a subject withdraws or the investigator discontinues subject participation after Visit 1, data from that visit will be included in the analysis of Objective 1, but not Objective 2

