8.1. Outcome Measures for Evaluation of Feasibility / Tolerability

Tolerability will be assessed and recorded by the following parameters:

- (1) Occurrence of drop-out
- (2) Adherence/compliance
- (3) Side effects (bloating, flatulence, belching, abdominal pain, discomfort, watery stool, and vomiting) will be monitored every week via text, email, or phone call using the PROMIS Gastrointestinal Symptom Scale.

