9.6. Missing data

We expect a 20% drop out during the proposed study. We assume the subjects will drop out randomly and all the missing data is missing completely at random (MCAR). In this case, we will implement complete-case analysis for the primary statistical analysis. However, we will also explore the possibility that the missing data is not MCAR. In the sensitivity analysis, we will compare the drop-out and non-drop group in terms of demographic characteristics and clinical factors. More specifically, we will perform two-group testing between the drop-out and non-drop group using either t-test, Wilcoxon test or chiq-square test depending on distribution and type of the variables of interest. If the missing data is indeed missing at random (MAR), we will perform multiple imputation method to generate the missing values with Rubin's rule to obtain the unbiased inference, which will be compared with results from the primary statistical results.

10. Safety Monitoring and Management

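### The noncompliance withdrawal rule in 6.7, read with 7.8 and 9.6, can discard later adherence data and week-4 samples from poor adherers, although adherence is a tolerability outcome

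*Combined protocol and SAP*

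**What the plan says.** - **Adherence as an outcome.** Section 4.3 says that "tolerability will be evaluated through occurrence of drop-out and adherence". Section 8.1 lists "Adherence/compliance" as the second of three tolerability parameters, after drop-out and before side effects.
- **How it is measured.** Section 6.6: "Participant adherence will be monitored weekly via email and/or text messages through self-reporting of number of treatment pouches left".
- **Missed doses.** Section 4.1 allows for them: "If participants miss taking a dose on a given day, they will be directed to put the pouch for that day aside", and the participant carries on with the next pouch.
- **Withdrawal.** Section 6.7 says that when "participant noncompliance increases risk of decreased study integrity, the participant will be withdrawn from the study". This is withdrawal from the study, not only from product, and no level of noncompliance is given.
- **Data after discontinuation.** Section 7.8 covers both participant withdrawal and discontinuation by the investigator after Visit 1: "data from that visit will be included in the analysis of Objective 1, but not Objective 2".
- **Missing data.** Section 9.6 assumes MCAR, and "we will implement complete-case analysis for the primary statistical analysis". Multiple imputation follows only if the data are judged MAR.
- **Analysis sets.** Section 9.2 names intent to treat once, for the Aim 1 count of participants with an adverse event. No analysis set or summary is named for adherence, and no set for Aim 2. Section 9.4 says that withdrawn participants are not replaced.

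**The concern.** A participant who leaves pouches untaken because the product disagrees with them is a case that an adherence measure of tolerability should capture. Under 6.7 that behaviour, if judged serious enough, ends the person's participation. A poor value on an outcome then decides whether further outcome data exist, which is selection on a variable measured after randomisation.

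Three results are at stake:

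- **Adherence.** A completer summary would leave out the lowest values.
- **Drop-out.** The heading of 6.8 equates drop-out with voluntary withdrawal. An investigator withdrawal for noncompliance may therefore not count as drop-out, and could be missing from both tolerability measures.
- **Aim 2.** The week-4 stool and blood results of those withdrawn are absent. If skipping is commoner on active product than on placebo, the arms compared are no longer the randomised groups.

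**Working it through.** **1. The plan's own figures.** Section 9.5 recruits 60 and expects 20% drop-out: 60 × 0.80 = 48, and 48 / 3 = 16 per arm. This reproduces. On this reading about 60 / 3 = 20 are randomised per arm and 16 are completers, so up to 12 participants (about 4 per arm) are expected to be absent from Aim 2. Noncompliance withdrawals would be among them. The synopsis instead treats 48 (16 per arm) as the number enrolled, so both 20 and 16 are used below.

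**2. What happens to a participant withdrawn for noncompliance.**

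| Item | Section | Result |
|---|---|---|
| Pouch counts before withdrawal | 6.6, 7.5 | Collected; no stated use in analysis |
| Pouch counts after withdrawal | 6.7 | Not collected |
| Objective 1 data | 7.8 | Literally Visit 1 only, which is Day 0, when product is handed out, so no adherence value exists |
| Counted as drop-out | 6.8, 8.1 | Unclear |
| Week-4 samples | 6.7 | Not collected |
| Objective 2 | 7.8, 9.6 | Excluded |

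The follow-up after withdrawal in 6.8 and 10.2 is by text or email and is written for participants who choose to leave. It does not clearly cover those whom the investigator withdraws. The table of events is broken in the text available, so nothing is inferred from it.

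**3. Is the missingness MCAR?** Under 6.7 the chance of being withdrawn depends on adherence, which may in turn depend on symptoms and on arm. That is not MCAR. The check in 9.6 compares demographic and clinical factors between those who drop out and those who do not. It does not name adherence or arm.

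**4. Size for adherence (illustration).** The documents give no adherence or noncompliance rate. Assume 95% in those who stay and *a* = 30–60% in *w* = 1–4 withdrawn participants out of *n* randomised in an arm.

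All-randomised mean = [(n − w) × 95 + w × a] / n. Overstatement if only completers are summarised = w × (95 − a) / n.

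| n | w | Mean, a = 60 | Gap | Mean, a = 30 | Gap |
|---|---|---|---|---|---|
| 20 | 1 | 93.25 | 1.75 | 91.75 | 3.25 |
| 20 | 2 | 91.50 | 3.50 | 88.50 | 6.50 |
| 20 | 4 | 88.00 | 7.00 | 82.00 | 13.00 |
| 16 | 1 | 92.81 | 2.19 | 90.94 | 4.06 |
| 16 | 2 | 90.63 | 4.38 | 86.88 | 8.13 |
| 16 | 4 | 86.25 | 8.75 | 78.75 | 16.25 |

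**5. Size for Aim 2 (illustration).** Let a share *s* of an arm be withdrawn for noncompliance, and suppose they would have shown a fraction *f* of the completers' mean change. The all-randomised mean change divided by the completer mean change is 1 − s × (1 − f).

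- s = 5%, f = 0.5: 1 − 0.05 × 0.5 = 0.975.
- s = 20%, f = 0: 1 − 0.20 × 1 = 0.80.

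Each such withdrawal removes 1/20 = 5% of an arm's Aim 2 data, or 1/16 = 6.25% if 16 are randomised.

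**The case against.** Several safeguards count against the point, and three stronger readings should be set aside.

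- **A reader might infer that adherence is measured only in adherers.** The documents do not say so. Weekly counts exist up to withdrawal, nothing states that they are discarded, and missed doses are tolerated. The literal Visit 1 reading of 7.8 also sits badly with the adverse-event count in all individuals in 9.2, so it may be loose drafting. What remains is that no adherence summary or set is defined, and the only sentence on use of discontinued participants' data points to a visit before dosing.
- **A reader might call Aim 2 a per-protocol comparison.** It has no adherence cut-off, and 6.7 keeps dose-reduced participants in the trial. It is a completer comparison, and 7.8 and 9.6 produce it for every kind of withdrawal. Changing 6.7 alone would not cure it.
- **A reader might see a breach of intent to treat.** That term in 9.2 covers adverse events only. No intent-to-treat analysis of adherence or Aim 2 is promised, so none is contradicted.

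It is also fair to say that noncompliance in 6.7 is not defined as skipping product; that symptoms are collected weekly and separately from pouch counts; that reasons for discontinuation and protocol departures are to be documented; and that 9.6 plans a drop-out comparison and conditional imputation. These limit the damage to the adverse-event results. They do not recover week-4 samples that were never taken, and imputation would depend on a MAR judgement that need not consider adherence. The biomarker work is described as exploratory, which lowers the stakes for Aim 2 but not for tolerability, the subject of Aim 1.

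**Conclusion.** The conflict is real and lies in the combination of 6.7, 7.8 and 9.6 with 4.3 and 8.1. Followed as written, the plan lets poor adherence end data collection, treats the resulting gaps as MCAR, and leaves open whether withdrawn participants enter the adherence and drop-out results.

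The size cannot be computed from the documents. Under the stated assumptions (95% adherence in those who stay, 30–60% in 1–4 withdrawn per arm), a completer summary overstates adherence by about 2 to 13 points with 20 randomised per arm, and 2 to 16 points with 16. If 9.5 is right that 16 is the number left after drop-out, the 20-per-arm range is the relevant one, because subtracting from 16 counts attrition twice. The overstatement arises only if adherence is summarised in completers. For Aim 2, the all-randomised change would be 0.80 to 0.975 of the completer change if 5–20% of an arm is withdrawn and would have shown 0–50% of the completers' change. The direction of any between-arm bias depends on whether skipping differs by arm, which is unknown.

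**What to change.** Reconcile 6.7, 7.8 and 9.6 with 4.3 and 8.1:

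1. **6.7.** Separate stopping product from ending data collection. Whether product continues stays with the clinical team. Where the participant agrees, keep the contacts and week-4 samples already scheduled, and record actual intake and the reason. Say what is meant by noncompliance.
2. **8.1 and 9.2.** Summarise adherence for all randomised participants by arm, including pouch counts up to any withdrawal, and state the denominator. Count investigator withdrawals for noncompliance, by arm, in the drop-out outcome, and align the wording of 6.8.
3. **7.8.** Replace the reference to a single visit, so that all data collected before and after discontinuation are used.
4. **9.2 and 9.6.** Analyse Aim 2 by assigned arm with all available week-4 data, and run a compliant-only analysis as sensitivity. Do not assume MCAR for noncompliance withdrawals; include adherence and arm in the drop-out comparison and in any imputation model.

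The cost is protocol and SAP wording, with no new visits. The downside is slight dilution of Aim 2 effects, which the compliant-only analysis would show.

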6.8. Voluntary Withdrawal (Drop-Out) of Enrolled Participants

Participants may voluntarily withdraw from study at any time, for any reason, with no penalty or loss of rights. Participants that choose to withdraw from the study will be followed up (via text or email communication) to determine safety based on frequency and severity of side effects. Reasons for discontinuation will be documented in the study RedCap database.

7. Study Procedures and Schedule

7.1. Table of Events

Procedures		Screening -Day -14 to 0)	Baseline (Study Visit 1)	Phone Contact 1 (Day 0 + 7±2)	Phone Contact 2 (Day 0 + 14±2)	Phone Contact 3 (Day 0 + 21±2)	Final Visit (Day 0 + 28±2)	Follow-up Contact (Day 0 + 35±2)	Premature Discontinuation
Eligibility Assessment	X								
Informed Consent	X								
Medical History	X						X		X
Concomitant Medications	X						X		
Study Intervention		X	X	X	X	X	X		
Adherence Evaluation			X	X	X	X	X		
Assessment of Adverse Events			X	X	X	X	X	X	X
35-question PROMIS Gastrointestinal Symptom Scale (Appendix 1)		X	X	X	X	X	X	X	X
Research Laborato ry	Phlebotomy	X					X		
	Immunology - serum	X					X		
	Microbiome - stool	X					X		

Procedures	Screening -Day -14 to 0)	Baseline (Study Visit 1)	Phone Contact 1 (Day 0 + 7±2)	Phone Contact 2 (Day 0 + 14±2)	Phone Contact 3 (Day 0 + 21±2)	Final Visit (Day 0 + 28±2)	Follow-up Contact (Day 0 + 35±2)	Premature Discontinuation
Intestinal barrier function - serum		X				X		

7.2. Enrollment/Pre-Screening (Day -14 to 0)

Screening to determine eligibility and if applicable, consent processes will be performed virtually on zoom. Within 2 weeks, blood sample collection, food questionnaire and stool collection kit will be provided on day 0.

7.3. Screening (Day -14 to 0)

Activities to be performed at screening:

- (1) obtain consent,
- (2) schedule study visits
- (3) provide participant instructions

7.4. Visit 1 (Day 0, Baseline)

- (1) schedule study visits/communications
- (2) provide participant instructions
- (3) collect blood sample for research only
- (4) provide food questionnaire link and food diary booklet
- (5) Gastrointestinal Symptom and Severity Checklist
- (6) provide stool collection kit and mailing instructions for return
- (7) provide intervention packets for 28 days

7.5. Phone Contact (Day 0 +7±2, Day 0 + 14±2, Day 0 + 21±2, and Day 0 + 35±2)

Information to be collected at days 7±2, 14±2 and 21±2:

- (1) Follow-Up Phone Script
- (2) Participant's compliance with intervention (adherence)
- (3) Gastrointestinal Symptom and Severity Checklist - symptom rating
- (4) Record adverse events as reported by subject

7.6. Final Visit (Day 0 +28±2)

Visit 2 (V2) will be the final visit of the study. The following will be conducted during this visit:

- (1) Collect blood sample
- (2) Provide food frequency questionnaire
- (3) Provide stool collection kit and mailing instructions for return
- (4) Gastrointestinal Symptom and Severity Checklist
- (5) Record adverse events as reported by subject
- (6) Record subject's compliance with intervention (adherence)
- (7) Collect leftover intervention packets

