Where the K_m factor is a number based on body surface area. In our animal study we used a dose of 1,500 mg kg⁻¹, based on ~30 mg LacNAc fed to a ~20 g mouse per day²⁵. We used a K_m factor of 3 for mice and 37 to represent a 60 kg human adult.

We can consistently produce hGOS containing concentrations that exceed 25 g/L of LacNAc with no significant variation between batches observed. Therefore, our approach is to normalize to reach the proposed dose levels using pure GOS. The active component is in power form that will be obtained after lyophilization. Concentration will be confirmed using previously developed HPLC protocols³³

Acquisition: [name], Professor of Plant and Microbial Biology at North Carolina State University and Co-investigator in this proposal, will coordinate with the Golden LEAF Biomanufacturing Training and Education Center (BTEC) the cGLP production of the prebiotics galacto-oligosaccharides (GOS) and GOS enriched in N-acetyl-D-lactosamine (LacNac, humanized GOS, hGOS) for the clinical intervention planned for the study. BTEC has the capabilities, equipment, and expertise for the bioprocess cGLP production (See Appendix 1).

Formulation/Packaging/Labeling: GOS, hGOS, and placebo will be supplied as a sterile powder by BTEC, dried and portioned into daily dose pouches under sterile conditions at the NC Food Innovation Lab, Kannapolis, NC, . Pouches will be labeled and will serve to protect the preparations from light, air,

Protocol Number:
Study Acronym: GOS Pilot

Enrollment ID:

Lot No.:

Subject Number:

Subject's Initials:

Date Dispensed:

Contents: 56 pouches, 5 g each for the first 10 days followed by 7.5 grams each for days 11-28 of GOS, hGOS or matching placebo, plus two additional packets (one 5mg and one 7.5mg) for inadvertent loss or spillage.

Directions: Use only as directed. To be taken by mouth with food or beverage.

This product is an investigational product to be dispensed only by a qualified investigator.

Storage: Room Temperature 15-30 °C (59-86°F)

Caution: New drug limited by law to investigational (clinical trial) use only. Keep out of reach of Children.

Manufactured By: Golden LEAF Biomanufacturing Training and Education Center (BTEC), [name]

Distributed by:

and moisture. Product will then be transferred to the UNC Investigational Drug Services (IDS).

Storage and Stability:

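### Because each stool kit is handed out only at its own visit, a home baseline sample can come after dosing starts and a home final sample any number of days after it ends

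*Combined protocol and SAP*

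**What the plan says.** Section 4.3 sets blood and stool collection at Day 0 and Day 28 and describes the kit as a back-up: "Stool collection kits will be provided to participants in case samples cannot be obtained" at the visit itself. Section 7.2 confirms that the "stool collection kit will be provided on day 0".

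The visit lists then give the sequence:

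- Section 7.4 (Visit 1, Day 0), items 6 and 7: "provide stool collection kit and mailing instructions for return", followed by "provide intervention packets for 28 days".
- Section 7.5 (phone contacts): no kit is sent.
- Section 7.6 (Final Visit, Day 28±2), items 3 and 7: "Provide stool collection kit and mailing instructions for return" and "Collect leftover intervention packets".

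Visit 1 lists a single kit, so the Final Visit is the first listed hand-out of the end-of-treatment kit.

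The Synopsis and Section 2.3 place the baseline assessment ahead of treatment, and the second one in week 4 once the prebiotic has been taken. Section 7.9 expects participants to mail stool samples and provides a label with visit, date and place of collection. Section 9.2 (A2.1) tests baseline against week 4 within each arm by matched-pair Wilcoxon tests, and compares the change across arms by Kruskal-Wallis.

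**The concern.** A participant who cannot produce stool at Visit 1 leaves with both the kit and the product. The visit list does not say that the sample comes before the first pouch. A participant who cannot produce stool at the Final Visit receives the kit when the product is taken back, so that sample necessarily follows the last dose, by a delay that no section limits.

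The abundance of *Bifidobacterium* and *Akkermansia* is one of the three secondary components in Section 4.4, and A2.1 analyses it as a change from baseline. If a prebiotic effect builds up on product and fades off it, a late baseline and a late final sample err in the same direction. Both make the measured change smaller in the active arms and should matter little under placebo. The comparison with placebo is then pulled toward no difference. A mistimed sample cannot be retaken afterwards.

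**Working it through.** **1. Product supply.** The label in Section 6.1 reads "Contents: 56 pouches, 5 g each for the first 10 days followed by 7.5 grams each for days 11-28". At two pouches a day, 10 × 2 + 18 × 2 = 20 + 36 = 56, which reproduces the stated count. The two extra pouches replace lost or spilled product. Section 4.1 has a missed pouch set aside, so missed doses do not lengthen the schedule. Scheduled dosing therefore ends on day 28.

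**2. Timing of a home final sample.** Let V be the visit day (26 to 30) and L the days from visit to stool. The documents give no L, so the values below are assumptions. Days since the last dosing day = (V − min(V, 28)) + L. Regular pouches left on day 26 are 56 − (20 + 2 × 16) = 4.

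| Visit day | Regular pouches left | L = 0 | L = 1 | L = 3 | L = 7 |
|---|---|---|---|---|---|
| 26 | 4 | 0 | 1 | 3 | 7 |
| 28 | 0 | 0 | 1 | 3 | 7 |
| 30 | 0 | 2 | 3 | 5 | 9 |

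After a Day 28 visit, any L of 1 or more falls outside week 4, and L of 3 or more falls beyond the last day of the visit window (day 30).

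**3. Timing of a home baseline sample.** Dosing runs from day 1. A stool on Day 0 is clean. One taken 1, 3 or 7 days later falls during dosing day 1, 3 or 7, unless day 1's sample precedes the first pouch.

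**4. Direction.** Write E for the full effect, r for the fraction still present at the final sample, and b for the fraction already present at baseline. The measured change is E × (r − b), against E for correctly timed samples. Any r below 1 or b above 0 reduces it.

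**5. Size, by illustration only.** The documents give no washout rate, home-sample share or delay. Assume exponential washout, r = 2^(−delay / half-life), with half-lives of 2, 3 and 7 days:

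| Delay | 2 days | 3 days | 7 days |
|---|---|---|---|
| 1 day | 0.71 | 0.79 | 0.91 |
| 3 days | 0.35 | 0.50 | 0.74 |
| 5 days | 0.18 | 0.31 | 0.61 |

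If a share h of active-arm final samples is late and baselines are clean, the average effect is multiplied by f = 1 − h(1 − r), and the equivalent size per arm is about 16 × f²:

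| r | h = 25%: f | h = 25%: n | h = 100%: n |
|---|---|---|---|
| 0.91 | 0.9775 | 15.3 | 13.2 |
| 0.74 | 0.935 | 14.0 | 8.8 |
| 0.50 | 0.875 | 12.3 | 4.0 |
| 0.18 | 0.795 | 10.1 | 0.5 |

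With h = 0 the figure stays at 16. The last column is an extreme in which every active-arm final sample is equally late.

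In terms of power, take a two-sided 5% test, 16 per arm, the normal approximation and a true standardized difference of 0.991, which gives 80%. Shrinking the difference by 10%, 20% or 30% lowers power to about 71%, 61% or 50%. These are mean-shift approximations, whereas A2.1 uses rank tests. No figure for b can be offered.

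**The case against.** The strongest reply is that the plan already states the intended timing and treats the kit as an exception. Section 4.3 makes it a back-up, the flow diagram shows stool collected at 4 weeks, and the Table of Events schedules stool at two time points. A sample given at the visit does not depend on when the kit was handed out, and a same-day home sample after a Day 26 to 28 visit has almost no gap. This stands, and it confines the point to home samples. It does not show that they are rare. Sections 7.4 and 7.6 list collecting blood but, for stool, only a kit and mailing instructions. Section 7.9 likewise contrasts blood drawn on site with stool sent by mail. The share is unknown.

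Three stronger readings are tempting, and the documents do not support them:

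- A reader might infer that the plan requires no pre-treatment baseline. The Synopsis and Section 2.3 do require one, and Section 4.3 fixes Day 0. The participant instructions, whose content is not shown, might also cover the order. What is missing is a working rule where the kit is handed out.
- A reader might infer that any final sample after the last dose breaches the plan. The plan itself puts the second assessment after the treatment. The defect is that the gap has no limit.
- A reader might infer that the trial shrinks to about 4 per arm. That needs every active-arm final sample to be 3 days late with a 3-day half-life, and nothing in the documents supports any of these assumptions.

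A Day 30 visit, two days after scheduled dosing ends, reflects an ordinary visit window that applies equally to blood and has nothing to do with kit hand-out. The dated label in Section 7.9, and the general commitment to sensitivity analyses in Section 9, already supply part of a remedy. However, no dose time is linked to the label, and no rule says which samples count as mistimed.

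**Conclusion.** The point holds for participants who use the home kit. Followed as written, Sections 7.4 and 7.6 allow a baseline sample after dosing has begun and place every home final sample after product has been taken back, with no upper limit on the delay. Neither is sure to fall within the timing stated in Sections 2.3 and 4.3.

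The direction, dilution toward zero in the GOS and hGOS arms, rests on the assumption that the effect accumulates on product and fades off it. The size is not derivable. At an assumed 25% home share, the illustration runs from about 15 down to about 10 effective participants per arm. The loss is nil if all samples are given at the visits. The equivalent-size figures should not be cited without those assumptions.

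The effect is limited to the secondary microbiome outcome, for which Section 9.5 sets the size by funding and states no power target. The primary tolerability outcome is unaffected. This is a cheap improvement worth making, and it does not show that the trial fails.

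**What to change.** - **Sections 7.2, 7.4 and 7.6:** supply each kit ahead of its visit. The baseline kit goes out after consent and before Day 0. The final kit is given at Visit 1 or mailed before Day 28. The sample can then be brought to the visit or mailed by that date.
- **Section 4.3:** state that the baseline stool is collected before the first pouch, and the final stool within a fixed short window around the last scheduled dose. Reconcile that window with the existing wording that places the second assessment in week 4 and after the treatment.
- **Section 7.9:** add the date and time of the first and last dose to the sample date and collection place already recorded.
- **Section 9.2 (A2.1):** define out-of-window samples and pre-specify a sensitivity analysis that excludes them. Report their number by arm and time point. Lateness may itself be related to bowel habit, so this analysis should accompany the main one and not replace it.

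The cost is a few lines of text, two dose-time fields and some postage, since screening is virtual. Section 7.9 allows storage at ambient temperature for up to 2 years, so earlier collection is practicable. Some kits sent early may be mislaid and need replacing. Doses and the treatment schedule are unchanged.
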